2.2 Secondary objectives

- To potentially evaluate the effect of autologous platelet transfusions in healthy volunteers at either 12, 24 or 48 hours after a loading dose of clopidogrel on platelet inhibition as measured by LTA²
- To evaluate the effect of autologous platelet transfusions in healthy volunteers at 24 and 48 hours (and potentially 12 hours) after a loading dose of ticagrelor on platelet inhibition as measured by VerifyNow™
- To potentially evaluate the effect of autologous platelet transfusions in healthy volunteers at either 12, 24 or 48 hours after a loading dose of clopidogrel on platelet inhibition as measured by VerifyNow™
- To evaluate the durability of restoration of platelet aggregation following platelet transfusion

² If the 24-hour and 48-hour cohorts are both successful, a platelet transfusion at 12 hours after the loading dose of ticagrelor (Day 1) in a single treatment, without crossing over to a non-transfusion period, hence a parallel group, will be performed.

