5.5.3 Doses and treatment regimens

Each healthy volunteer will be administered 180 mg ticagrelor or 600 mg clopidogrel, orally, as a single administration on Day 1 of each treatment period, based on the randomization scheme and cohort assignment. The investigational product will be administered after an overnight fast of at least 10 hours and at least 4 hours for cohorts 3a and 4a. For cohort 3a (platelet transfusion at 12 hours) ticagrelor will be administered in the evening. The 180 mg loading dose ticagrelor administrations will be separated by a washout period of at least 14 days.

Background ASA (81 mg once daily) will be administered from either Day -2 (cohort 1) or Day -1 (cohort 2). The ASA administration will commence immediately after the platelet apheresis. The administration and duration of the ASA background treatment will be dependent on the transfusion cohort the healthy volunteer is allocated to ([Table 1](#)).

Each healthy volunteer will have a platelet apheresis either on Day -2 for cohort 1, or on Day -1 for cohort 2, and one autologous apheresis platelet unit transfusion during one of the treatment periods at either 24, 48, or 12 hours based upon the cohort assignment.

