The Investigator will assess causal relationship between investigational product and/or additional study drug and each AE, and answer ‘yes’ or ‘no’ to the question ‘Do you consider that there is a reasonable possibility that the event may have been caused by the investigational product and/or additional study drug?’

For SAEs causal relationship will also be assessed for other medication, study procedures, and additional study drug. Note that for SAEs that could be associated with any study procedure the causal relationship is implied as ‘yes’.

A guide to the interpretation of the causality question is found in [Appendix B](#) to the CSP.

Adverse Events based on signs and symptoms

All AEs spontaneously reported by the healthy volunteer or reported in response to the open question from the study personnel: ‘*Have you/the child had any health problems since the previous visit/you were last asked?*’, or revealed by observation will be collected and recorded in the eCRF. When collecting AEs, the recording of diagnoses is preferred (when possible) to recording a list of signs and symptoms. However, if a diagnosis is known and there are other signs or symptoms that are not generally part of the diagnosis, the diagnosis and each sign or symptom will be recorded separately.

Adverse Events based on examinations and tests

The results from protocol mandated laboratory tests and vital signs will be summarized in the Clinical Study Report (CSR). Deterioration as compared to baseline in protocol-mandated laboratory values, and vital signs should therefore only be reported as AEs if they fulfil any of the SAE criteria or are the reason for discontinuation of treatment with the investigational product.

If deterioration in a laboratory value/vital sign is associated with clinical signs and symptoms, the sign or symptom will be reported as an AE and the associated laboratory result/vital sign will be considered as additional information. Wherever possible the reporting Investigator

uses the clinical, rather than the laboratory term (eg, anemia versus low hemoglobin value). In the absence of clinical signs or symptoms, clinically relevant deteriorations in non-mandated parameters should be reported as AE(s).

Any new or aggravated clinically relevant abnormal medical finding at a physical examination as compared with the baseline assessment will be reported as an AE.

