12.2.2 Safety Analyses

All safety data (scheduled and unscheduled) will be presented in the data listings. Continuous variables will be summarized by cohort, treatment, and time point using descriptive statistics (n, mean, SD, minimum, median, maximum). Categorical variables will be summarized by cohort, treatment, and time point in frequency tables (frequency and proportion). Safety variables (eg, clinical laboratory values and vital signs) will be reported to the same precision as the source data. Derived variables will be reported using similar precision to those from which they were derived (eg, QTc derived from QT interval).

Extra measurements (such as unscheduled or repeat assessments) will not be included in the descriptive statistics by scheduled time point, but will be included in data listings. All AEs, ECG outliers, and clinical laboratory outliers that occur following the first administration of the investigational product will be included in the tabulations of AEs and outlier events, including episodes that occur at unscheduled evaluations.

All available data from volunteers in the safety analysis set will be included in the safety analyses. No adjustment or imputation will be utilized for missing values or for volunteers who withdraw prior to completing the study, neither will analyses be restricted to volunteers with complete data.

All AEs will be collected for each volunteer from the time when informed consent is obtained until the follow-up visit. Adverse events that occur before dosing will be reported separately.

Adverse events will be summarized by Preferred Term and System Organ Class using Medical Dictionary for Regulatory Activities (MedDRA) vocabulary (Version 12.0 or higher) by cohort and treatment, and across cohorts and all treatments, as appropriate. Furthermore, listings of SAEs and AEs that lead to withdrawal will be presented and the number of volunteers who have any AEs, SAEs, AEs that lead to withdrawal, and AEs with severe intensity will be summarized.

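### Section 6.4.3: the discontinuation route to AE status closes after the last single dose and never covers a stopped or withheld apheresis or transfusion

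*Protocol*

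**What the plan says.** Protocol 6.4.3 states that results of mandated laboratory tests and vital signs will be summarised in the study report, and for that reason a deterioration from baseline in them should "only be reported as AEs if they fulfil any of the SAE criteria or are the reason for discontinuation of treatment with the investigational product".

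The same section leaves other routes open. If the deterioration comes with clinical signs or symptoms, "the sign or symptom will be reported as an AE and the associated laboratory result/vital sign will be considered as additional information", and the clinical term is preferred ("eg, anemia versus low hemoglobin value"). Clinically relevant new or worsened findings at physical examination are AEs, as are events revealed by observation. For non-mandated parameters without symptoms, clinical relevance alone is enough.

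The investigational product is given "as a single administration on Day 1 of each treatment period" (5.5.3). Cohort 3a is run "in a single treatment, without crossing over to a non-transfusion period, hence a parallel group" (2.2, footnote). Table 6 lists ticagrelor as the investigational product. Table 7, titled as additional study drugs, lists ASA and clopidogrel. Section 5.8 deals with discontinuing investigational product and says nothing about an interrupted apheresis or transfusion.

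On reporting, 12.2.2 says that unscheduled or repeat measurements "will not be included in the descriptive statistics by scheduled time point". They are listed. The next sentence brings ECG and clinical laboratory outliers into the tabulations, unscheduled ones included. It does not name vital signs.

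**The concern.** The discontinuation trigger is natural under repeated dosing, where there is always a next dose to stop. Under single dosing it works only while a dose is still to come. The same asymptomatic, non-serious change can therefore be an AE in Period 1, if the Period 2 dose is withheld because of it, and cannot be one after the Period 2 dose or after the only dose in cohort 3a.

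The safety objective (2.3) is to describe tolerability of a loading dose given before an autologous platelet transfusion. Section 1.4 names hypotension, during or immediately after transfusion, among the possible signs of bacterial contamination of platelets. A change that stops the transfusion is the kind of event this objective should count, yet stopping the transfusion does not make it one. Apheresis and transfusion belong to Treatment A only, so whatever this part of the rule leaves out is missing from one column of the AE tables by treatment.

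**Working it through.** The plan gives no figure to reproduce. The check is a count of remaining doses, a reading of the other routes to an AE, and the timing of vital signs.

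**1. Doses left to discontinue** (planned doses minus doses given; 5.5.3, 2.2 footnote, 5.2.1)

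| Situation | Doses left | Discontinuation route |
|---|---|---|
| Crossover, after Period 1 dose | 2 − 1 = 1 | open |
| Crossover, Period 2, before dose | 2 − 1 = 1 | open |
| Crossover, after Period 2 dose | 2 − 2 = 0 | closed |
| Cohort 3a, before dose | 1 − 0 = 1 | open |
| Cohort 3a, after dose | 1 − 1 = 0 | closed |

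The pre-dose rows matter because 6.4.3 collects AEs from Day -2, and apheresis is on Day -2 or Day -1 (Table 1, footnote j). A change between apheresis and dosing can still lead to the dose being withheld.

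**2. Cohort 3a, Table 4.** Post-dose mandated safety assessments are one blood count at 12 h, three platelet counts, vital signs at 24, 48 and 72 h, and laboratory tests at 84 h: 1 + 3 + 3 + 1 = 8. No dose remains at any of them, so the route can be met at 0 of 8.

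**3. Does ASA keep the route open?** The first column of Table 7 is headed as investigational product, so ASA could loosely be counted as one. In cohort 2 the last ASA dose is on Day 2 (24 h) and the transfusion is at 48 h. In cohorts 1 and 3a the last ASA dose is on Day 1, before the transfusion. On either reading nothing is left to discontinue after the transfusion once the last loading dose has been given.

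**4. What is left uncovered.** With the route closed, an AE still arises if the change is serious (6.4.2, including the important-medical-event criterion) or comes with a sign or symptom. What remains is the asymptomatic, non-serious change.

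**5. Vital signs around the transfusion.** Section 6 places vital signs before blood sampling at each time point, and the platelet samples at the transfusion hour are pre-transfusion.

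| Cohort | Transfusion | Next scheduled vital signs | Gap from start |
|---|---|---|---|
| 1 (Table 2) | 24 h | 48 h | 24 h |
| 2 (Table 3) | 48 h | 72 h | 24 h |
| 3a (Table 4) | 12 h | 24 h | 12 h |

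The transfusion lasts about 30 minutes (3.1). A reading during or soon after it is therefore unscheduled. It stays out of the descriptive statistics and is not among the tabulated outliers, which leaves the listings.

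**6. Share of transfusions with no later dose.** Cohorts 1 and 2 have 24 transfusions; with balanced sequences (an assumption, since 5.2.1 gives no ratio) 12 fall in Period 2. Cohort 3a adds 12.

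- Cohorts 1, 2 and 3a: (12 + 12) / 36 = 67%
- With 4 of 12 per crossover cohort transfused in Period 2: (8 + 12) / 36 = 56%
- With 8 of 12: (16 + 12) / 36 = 78%
- Cohorts 1 and 2 only: 12 / 24 = 50%

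**The case against.** The strongest defence is that the rule is a deliberate convention with a stated reason: mandated results are reported elsewhere and need not be repeated as AEs. There are real backstops. Changes from baseline are summarised by cohort and treatment, abnormal laboratory values are flagged and outliers tabulated (12.2.2), the sponsor reviews laboratory and vital-sign data for other significant AEs (11.1.1), and clinically significant laboratory results are repeated and followed (6.4.5). The objective is descriptive, and because sequence is randomised the period dependence does not by itself favour either treatment in the crossover cohorts. It is also unclear whether an unscheduled reading during transfusion counts as protocol-mandated at all; if not, clinical relevance alone would make it an AE.

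Most of this stands, and it rules out several stronger readings that a reader might infer:

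- *Non-serious deteriorations cannot be AEs after the last dose.* Not so: those with signs or symptoms are AEs under the next paragraph of 6.4.3.
- *The route is shut throughout cohort 3a and Period 2.* Not so: it is open until the dose is given.
- *Unscheduled laboratory values vanish from the tables.* Not so: 12.2.2 tabulates laboratory outliers from unscheduled evaluations.
- *Mandated values should become AEs whenever clinically relevant, as non-mandated ones do.* The contrast is real, but adopting it would overturn the sponsor's convention, and the documents do not show that convention to be wrong.

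The defence does not answer two things. The stated reason relies on summaries, and those do not include unscheduled vital signs around the transfusion. Nor does anything in 6.4.3 treat an interrupted apheresis or transfusion as a trigger, although both are part of the treatment being described.

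**Conclusion.** The concern holds in a limited form. For asymptomatic, non-serious changes in mandated laboratory values or vital signs, the only route to an AE is discontinuation of the investigational product. That route is closed after the only dose in cohort 3a and after the Period 2 dose in the crossover cohorts, and it never covers the apheresis or transfusion. Recording therefore depends partly on the period in which the event falls. Data are not lost. What suffers is AE ascertainment, chiefly for vital signs around the transfusion, which reach only the listings unless the discretionary review for other significant AEs picks them up.

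The 67% (56% to 78% if sequences are unbalanced as shown) is the share of transfusions with no later dose. It assumes that cohort 3a is run, which requires cohorts 1 and 2 both to succeed. It should not be read as a rate of missed events: the protocol gives no event rate, and the number affected may be small. This is a cheap improvement, not a threat to the trial's conclusions.

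**What to change.** In 6.4.3, extend the second condition to read: *or are the reason for stopping, delaying or not giving the investigational product, an additional study drug, the platelet apheresis or the platelet transfusion*. Align the eCRF instructions. Naming the additional study drugs also removes the ambiguity between the title and the column header of Table 7.

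The change concerns AE recording only; it alters no dose, procedure or stopping decision. It leaves the sponsor's convention in place for mandated values that have no such consequence. The cost is one sentence, an update to the eCRF instructions, and a few more non-serious AEs to record.

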6.4.4 Reporting of serious adverse events

All SAEs have to be reported, whether or not considered causally related to the investigational product, or to the study procedure(s). All SAEs will be recorded in the eCRF.

If any SAE occurs in the course of the study, then Investigators or other site personnel inform appropriate AstraZeneca representatives immediately, or **no later than 24 hours** of when he or she becomes aware of it.

The designated AstraZeneca representative works with the Investigator to ensure that all the necessary information is provided to the AstraZeneca Patient Safety data entry site **within 1 calendar day** of initial receipt for fatal and life threatening events **and within 5 calendar days** of initial receipt for all other SAEs.

For fatal or life-threatening AEs where important or relevant information is missing, active follow-up is undertaken immediately. Investigators or other site personnel inform AstraZeneca representatives of any follow-up information on a previously reported SAE immediately, or **no later than 24 hours** of when he or she becomes aware of it.

6.4.5 Laboratory safety assessment

Blood and urine samples for determination of clinical chemistry, hematology, and urinalysis will be collected at the times indicated in the Study Plan ([Table 1](#)). The date and time of collection of all laboratory tests will be recorded in the appropriate eCRF.

The following laboratory variables will be measured:

Clinical chemistry

Serum (S)-Albumin

S-Alanine aminotransferase (ALT)

S-Aspartate aminotransferase (AST)

S-Alkaline phosphatase (ALP)

S-Bilirubin, total

S-Calcium, total

S-Creatinine

S-Fasting glucose

S-Potassium

S-Sodium

Coagulation

International normalised ratio (INR)

Activated partial thrombin time (aPTT)

Thrombin time (TT)

Partial prothrombin time (PT)

Hematology

Blood (B)-Hemoglobin

B-Leukocyte

B-Absolute leukocyte differential count

B-Platelet count

Urinalysis

Urine (U)-Glucose

U-Hemoglobin

U-Protein

Urine Drug Screen

All healthy volunteers will be tested for HIV, hepatitis B surface antigen and antibodies to hepatitis C at screening. In addition, a stool sample will be collected at screening for the detection of any blood present in the stool (fecal occult blood test).

Healthy volunteers enrolled in the relevant clopidogrel cohort should also have been tested regarding their CYP2C19 genotype status.

Urine samples will be screened for alcohol, cotinine, and drugs of abuse at screening (Day -30 to Day -3 and at Day -2). Urine will be tested for the following drugs of abuse: amphetamines, barbiturates, tricyclic anti-depressants, cocaine, methadone, morphine, tetrahydrocannabinol, and opiates. A pregnancy test (as part of the clinical chemistry sample) will be performed at screening and Day -2 for all females. FSH and LH levels of females considered to be of non-childbearing potential will be determined at screening.

Laboratory values outside the reference limit suspected to be of any clinical significance will be repeated. Healthy volunteers, for whom clinical significance is confirmed, will either not be included in the study or if already enrolled, will be monitored until normalisation or for as long as the Investigator considers necessary. Additional laboratory assessments may be performed for safety reasons if judged necessary by the Investigator.

The safety laboratory samples will be analyzed using routine methods at the Physician's Reference Laboratory.

Plateletpheresis will be performed at the Community Blood Center, whilst the platelet transfusion will be performed at St. Luke's South Hospital,

NB. In case a healthy volunteer shows an AST or ALT $\geq 3 \times \text{ULN}$ or total bilirubin $\geq 2 \times \text{ULN}$ please refer to [Appendix D](#) 'Actions required in cases of combined increase of Aminotransferase and Total Bilirubin – Hy's Law', for further instructions.

For blood volume see Section 7.1.

6.4.6 Physical examination

A complete physical examination will be performed as indicated in the Study Plan ([Table 1](#)) and include an assessment of the following: general appearance, respiratory, cardiovascular, skin, head and neck (including ears, eyes, nose, mouth, and throat), lymph nodes, thyroid, abdomen, musculoskeletal (including spine and extremities), and neurological systems.

A brief physical examination (including general appearance, skin, abdomen, cardiovascular and respiratory systems) will be performed on the days of the residential periods and at discharge from the clinic. In the study database only information whether the assessment was performed or not is to be recorded as well as any AEs.

Height will be measured in centimetres and weight in kilograms. All weight measurements should be taken without shoes on a calibrated scale. The BMI will be calculated from the height and weight.

6.4.7 ECG

Electrocardiograms will be performed at the time points indicated in [Table 1](#).

6.4.7.1 Resting 12-lead ECG

A 12-lead paper ECG for safety review by the Investigator will be performed after 10 minutes supine rest and the outcome of the overall evaluation is to be recorded as normal/abnormal in the eCRF, with any abnormalities specified. The print-out of the ECG is to be signed, dated, and filed in the Investigator's Study File.

6.4.8 Vital signs

Supine blood pressure will be measured using a semiautomatic blood pressure recording device with an appropriate cuff size. The healthy volunteers will be required to rest in a supine position for at least 10 minutes prior to blood pressure, and pulse rate measurements. For timings of assessments refer to the Study Plan ([Table 1](#)).

6.4.8.1 Pulse and blood pressure

Blood pressure (DBP and SBP) and pulse rate will be measured using standard equipment with an appropriate cuff size after 10 minutes supine rest on a bed. For timing of the measurements see the Study Plan (Table 1).

6.5 Patient reported outcomes (PRO) (Not applicable)

6.6 Pharmacodynamics

6.6.1 Collection of pharmacodynamic markers

Blood samples will be collected to determine IPA (by LTA and VerifyNow™) as outlined in Table 2 to Table 5. The measurement of platelet aggregation will be done at the Phase I Unit, Quintiles

Samples will be collected, labelled, stored and processed as detailed in the Laboratory Manual.

For blood volume for LTA and VerifyNow see Section 7.1.

6.7 Pharmacogenetics

6.7.1 Collection of pharmacogenetic samples

All healthy volunteers screened for the study will have to donate a blood sample for the mandatory pharmacogenetic analysis, if they are to be screened for the relevant clopidogrel cohort. Healthy volunteers needed for the relevant clopidogrel cohort will be assessed for their CYP2C19 genotype status to ensure that they carry 2 functional (*1) alleles (2C19 *1/*1). Blood samples for this analysis will only be collected after the healthy volunteer has provided a separate genetic informed consent for the genetics sample collection.

Blood samples will be collected during the pre-screening period (Days -35 to -30) to ensure that the results will be available in time to determine if the healthy volunteer could be enrolled in the study.

Healthy volunteers will be excluded from participating in the study if they refuse to consent to the genetic analysis.

The analysis and results from the pharmacogenetic testing will be used to determine which healthy volunteers will be eligible for the relevant clopidogrel cohort (cohort 3b, cohort 4a, or cohort 4b).

Only 1 sample should be collected per healthy volunteer (relevant clopidogrel cohort only) for genetic research during the study.

Samples will be collected, labelled, stored and shipped as detailed in the Laboratory Manual.

For blood volume see Section 7.1.

6.8 Health economics (Not applicable)

7. BIOLOGICAL SAMPLING PROCEDURES

7.1 Volume of blood

The total volume of blood to be drawn from each healthy volunteer included in this study is as follows:

Table 8 Volume of blood to be drawn from each healthy volunteer

Assessment		Sample volume (mL)	No. of samples	Total volume (mL)
Safety	Clinical chemistry	8.5	8	68
	Hematology	4	8	32
	Endocrinology	3.5	1	3.5
	Coagulation	2.7	8	21.6
Other	Virology	8.5	1	8.5
	Complete blood count	4	1	4
	Genotyping**	10	1	10
	Platelet counts	2	3	6
Pharmacodynamic				
	ADP - induced platelet aggregation (LTA)	4.5	29	130.5
	VerifyNow™ P2Y ₁₂ assay*	2	58	116
	Discard tube	2	28	56
Total				456.1

* VerifyNow™ samples will be collected in duplicate. The duplicate sample will only be used if the first sample is compromised

** Only for healthy volunteers screened for the relevant clopidogrel cohort

Table 9 Volume of blood to be drawn from each healthy volunteer for platelet apheresis

Assessment	Sample volume (mL)	No. of samples	Total volume (mL)
Platelet apheresis	250	1	250
Blood Center testing	45	1	45
Total			295 mL

